###### **Children and Adolescents**

Not applicable. We are only enrolling subjects 18 years of age and older.

###### **Adult Subjects Not Competent to Give Consent**

We are requesting a waiver of informed consent for this study but patients will still need to verbally opt in to text messaging. We plan to enroll only those patients who are competent at time of enrollment to opt-in for themselves.

## **2. Waiver of Consent**

### **Waiver or Alteration of Informed Consent\***

Waiver or alteration of required elements of consent.

#### **Minimal Risk\***

This study is minimal risk as all participants will be receiving standard clinical care. Colonoscopy is the standard of care for colorectal cancer screening, and all patients will receive standard bowel preparation instructions in addition to optional phone communication with endoscopy staff prior to the procedure. The only research-related activity is the randomization of participants to a text messaging program that will supplement routine practice when an individual schedules a colonoscopy at our institution. Since this study is intended to promote the standard of care for colorectal cancer screening, and the receipt of text messages poses negligible risk to the patient, we believe that waiver of consent is appropriate.

#### **Impact on Subject Rights and Welfare\***

Participation in the intervention is completely voluntary and subject rights and welfare will not be adversely affected by the waiver of authorization and consent. Participants randomized to the intervention arms still need to opt in to text messaging: Arm 1 will receive standard clinical care and Arm 2 will be enrolled into the text-messaging program in addition to standard clinical care. Placement in either arm for the purposes of research does not adversely affect the rights and welfare of the subjects, as each arm has the opportunity to engage in colorectal cancer screening, receive bowel preparation instructions, and communicate with the endoscopy staff over the phone. Randomly assigning patients to intervention and control does not alter patient's rights any differently than conducting an uncontrolled pilot study where some patients receive the intervention and some don't. We believe it is appropriate to obtain waiver of consent because learning the impact of different modalities for improving colorectal screening has significant potential clinical value for the practice (i.e. significantly increasing the rate of successful screening and thus decreasing the rate of mortality related to nonuse of screening).

#### **Waiver Essential to Research\***

The informed consent process itself may influence the outcome of our study, as it would require an additional phone call by the research coordinate to ask for participation. The purpose of the Way to Health text messaging program is to provide timely reminders regarding colonoscopy preparation. Obtaining waiver of consent would allow us to avoid the potential selection/volunteer bias for inclusion of patients who answer the phone and may be particularly motivated to complete colon cancer

screening. Since our main objective is to understand the potential influence of the text messaging intervention on colonoscopy show rate and adequate bowel preparation quality among all patients who agree to text messaging, we believe that obtaining informed consent separately from scheduling would not allow us to evaluate the impact of the intended intervention, which is text messaging navigation offered to all patients that agree during scheduling. Additionally, participants will be recruited via verbal communication when they call our institution call center to schedule their colonoscopy. We believe the research presents no more than minimal risk of harm to subjects and involves no procedures for which written consent is normally required outside of the research context.

#### **Additional Information to Subjects**

Participants randomized to the intervention arms will be informed that this program is voluntary and that they can stop participating in the program (stop receiving text messages) at any time.

#### **Written Statement of Research\***

No

#### **Risk / Benefit**

##### **Potential Study Risks**

The risks associated with this study are no more than minimal. There is the potential risk of breach of confidentiality involving medical records reviews or text messaging which will be maintained on the Way to Health platform. We will minimize this risk by using de-identified information whenever possible and by maintaining all identifiable information on a secure drive and/or in a HIPAA-compliant system (e.g. REDCap). In addition, all personnel will be held to high standards of upholding confidentiality and safeguarding patient privacy.

##### **Potential Study Benefits**

The benefits of this study for participants include a platform that may improve the bowel preparation experience prior to colonoscopy and increase the likelihood that a colonoscopy will not be hindered by inadequate preparation or a missed/canceled appointment. This will occur through a set of curated text messages with timely reminders as well as information with online links and a phone number to improve accessibility for questions to be answered on a timely basis. It is also possible that the benefits for some participants will be minimal. However, as mentioned, we believe the risks are also minimal. The control group is unlikely to directly benefit, as this group will continue to receive usual care. The potential public health impact of a successful intervention to improve colonoscopy show rates and bowel preparation quality is significant and could increase the chances of identifying colorectal cancer at an early stage and reduce the number of repeat colonoscopies and related costs due to inadequate bowel preparation. Information learned from this study may benefit society through a better understanding of how to

effectively increase the rate of adequate colonoscopies which could increase the rate of colorectal cancer screening and reduce the rate of mortality.

**Alternatives to Participation (optional)**

**Data and Safety Monitoring**

The study is minimal risk to participants and therefore the Principal Investigators and study team will monitor the safety of this study on an ongoing basis.

**Risk / Benefit Assessment**

The risks associated with this study are no more than minimal. Better knowledge on how to increase colonoscopy show rates and improve bowel preparation quality could potentially address one of the major barriers to appropriate colorectal cancer screening, which is the second leading cause of cancer death in the US. This study is designed to test an intervention with demonstrated feasibility and successful preliminary results in a small QI pilot. For these reasons and those outlined in the above benefits section, the investigators believe that the potential benefits outweigh the risks of participating in the study.

## Summary of Protocol Changes Modifications LOG

**Protocol:** Automated Text Message Navigation to Improve Outpatient Colonoscopy Show Rate and Bowel Preparation

**University of Pennsylvania Principal Investigator:** [name]

Date of Submission	Description of Modification	Rationale for Modification	Approval date
9/11/18	Initial submission		10/8/2018
10/22/18	Modification: - add staff (CRC) - add call center script		10/23/2018
11/14/18	Modification: - add recruitment by CRC & call script - change exclusion (from 10 to 14 days)		11/15/2018
12/19/18	Modification: - add patient recruitment flyer - modify CRC call script		12/19/2018
1/2/2019	Modification: - modify CRC call script - modify "welcome text" message for pts in intervention arm - modify inclusion/exclusion criteria - add description of procedure if arm 2 patient cancels or reschedules colonoscopy - add lead time of cancellation as an outcome measure (in days)		
4/4/2019	Modification: - modify sample size target - distinguish early and late phase enrollment		

## Initial Statistical Analysis Plan

The target enrollment sample size is 400 patients—200 in arm 1 (usual care) and 200 in arm 2 (usual care plus texting intervention). This number is based on sample size calculations using data from a previous pilot, which suggests that a total sample size of 200 patients will have greater than 80% power to detect a 15% difference in the primary outcome.

Descriptive analysis will include comparison of baseline demographics and major medical comorbidities between study arms. Continuous and categorical data will be compared using the Wilcoxon Rank-sum and Chi-squared tests, respectively. An alpha threshold of 0.05 will be used for statistical significance, with two-tailed testing performed in all instances. For the primary analysis, we will perform a Chi-squared test of independence to compare the proportion of colonoscopies with good/excellent bowel preparation between groups. In the secondary analysis, Chi-squared tests of independence will be performed to compare colonoscopy status (show, no-show, cancellation) as well as bowel preparation quality (excellent, good, fair, poor) between groups. Finally, among canceled colonoscopies, median lead time of cancellation will be compared between groups using the Wilcoxon Rank-sum test.

## Final Statistical Analysis Plan

**\*\*New changes from initial protocol notated in bold, parts removed from initial protocol notated in strikethrough**

The target enrollment sample size is 750 patients—375 in arm 1 (usual care) and 375 in arm 2 (usual care plus texting intervention). This number is based in part on sample size calculations using data from a previous pilot, which suggests that a total sample size of 750 patients will have greater than 80% power to detect a 10% difference in the primary outcome. We also chose a larger sample size to account for the fact that some patients enrolled in arm 2 may opt out of receiving text messages, which would likely decrease the effect size between arms.

Descriptive analysis will include comparison of baseline demographics and major medical comorbidities between study arms. Continuous and categorical data will be compared using the Wilcoxon Rank-sum and Chi-squared tests, respectively. An alpha threshold of 0.05 will be used for statistical significance, with two-tailed testing performed in all instances. For the primary analysis, we will perform a Chi-squared test of independence to compare the proportion of colonoscopies with good/excellent bowel preparation between groups. In the secondary analysis, Chi-squared tests of independence will be performed to compare colonoscopy status (show, no-show, reschedule, cancellation) as well as bowel preparation quality (excellent, good, adequate, fair, poor) between groups. Among canceled colonoscopies, median lead time of cancellation will be compared between groups using the Wilcoxon Rank-sum test. Finally, for both primary and secondary analyses, we will consider multivariable regression modeling to adjust for imbalances in possible confounders, if present despite randomization.

Deleted: 40  
Deleted: 200  
Deleted: 200  
Deleted: 20  
Deleted: 5  
Deleted: .

Deleted: Finally, a

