#### Primary outcome variable(s)

The primary outcome of the study will be colonoscopy show rate with good/excellent bowel preparation (binary).

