#### **Background**

Colorectal cancer (CRC) is the second leading cause of cancer death in the US, yet there are effective screening and treatment strategies that allow for early detection and treatment. CRC screening is recommended for all individuals aged 50-75, which could include stool testing or colonoscopy, but national rates are still suboptimal at 59-65%. Colonoscopy is an essential component of CRC screening, as it is also required if stool testing is positive. However, colonoscopy requires a complex process to identify an escort, purchase the preparation, take a day off from work, adhere to a clear liquid diet, and complete the split-dose preparation as recommended. This results in a significant no-show and cancellation rate, along with suboptimal preparation quality, which can lead to non-adherence and incomplete screening.

Current approaches to engaging patients include having nurses call patients before the procedure or patient navigators. However, it is often difficult to get patients on the phone, and these interventions can be costly, making it less scalable for clinical practices. Other interventions such as videos or mobile apps have been limited by poor user experience or limited engagement with the patient. There is an opportunity to leverage an automated text message navigation intervention using the Way to Health (WTH) platform to improve patient engagement prior to colonoscopy completion. The WTH platform is a Penn Medicine platform that is hosted on site at the University of Pennsylvania. The platform allows custom text messages to automatically be sent to patients, in addition to bidirectional message capabilities. WTH is protected by a secure firewall and is a HIPAA compliant platform.

In the past year, our team conducted a quality improvement pilot initiative using WTH that tested the feasibility and impact of a one-week text messaging protocol for patients who were scheduled for outpatient colonoscopy. The text messages sent to patients contained information about the preparation process and instructions, expectations about the procedure, and reminders about location and timing. Among the 21 patients enrolled in the pilot, we found high user acceptability and higher

colonoscopy show rates as compared to baseline values at PPMC (90% versus ~50%). As such we believe that the texting intervention is feasible for testing in the context of a randomized controlled trial.

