## Procedures

Screening – Phase 1: As above, patients will be screened and enrolled through one of two pathways (early and late phase). In the early phase (first 250 patients), a PPMC practice manager will forward a list of scheduled colonoscopies to the clinical research coordinator (CRC) on a regular basis. If patients are scheduled for colonoscopy in person while at the office, they will receive an informational flyer about the study that gives them the opportunity to contact a study team member for additional information or to enroll. It also informs them that someone from the study may contact them directly about participating. The CRC will screen patients for eligibility and make up to 3 phone call attempts to reach the patient. Once on the phone, the CRC will explain the details of the study using a script approved by the IRB and enter patients directly into the WTH platform for randomization. In the late phase (additional 500 patients), patients will be screened for eligibility through the same process as in the early phase. If they are scheduled for colonoscopy in person while at the office, they will also receive an informational flyer about the study that lets them know they may be contacted by text message about their upcoming procedure. For eligible patients, the CRC will then manually enter the validated patient cell phone number from the electronic medical record system into WTH. Randomization will then occur as described below, and intervention arm patients will receive two enrollment messages. These messages will describe the texting program and provide the opportunity for patients to opt out (by texting the word STOP). Of note, phone numbers will be confirmed to represent cell phones by using a publicly-available lookup utility. Importantly, patients who opt out will still be included in the intervention arm as an intention-to-treat analysis. Based on our experience with the QI pilot described above, we estimate needing to screen approximately 1,000 patients to meet our enrollment targets (750 total patients).

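### Does 750 patients fall short of the stated power of more than 80%, with nothing left over for opt-outs?

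*Combined protocol and SAP*

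**What the plan says.** The Final Statistical Analysis Plan sets 375 patients per arm and states that "a total sample size of 750 patients will have greater than 80% power to detect a 10% difference in the primary outcome". It continues: "We also chose a larger sample size to account for the fact that some patients enrolled in arm 2 may opt out" of the messages, which it expects to shrink the effect. The Target population section of the Final Protocol says much the same. On testing, the plan says: "An alpha threshold of 0.05 will be used for statistical significance, with two-tailed testing performed in all instances", with a chi-squared test for the primary comparison.

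The primary outcome is a yes/no composite: the patient attends and the preparation is good or excellent. The only baseline is in the Background section, where the pilot is reported to have had higher "colonoscopy show rates as compared to baseline values at PPMC (90% versus ~50" percent). The second figure is the site's usual show rate.

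Opt-out by text reply is described for the late phase, which supplies 500 of the 750 patients. The Procedures section adds that "patients who opt out will still be included in the intervention arm as an intention-to-treat analysis".

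**The concern.** The documents do not state the control rate behind the power figure. With a 50% show rate, the composite is 35% if 70% of attenders are well prepared and 45% if 90% are. In that region a 10-point difference is hardest to detect, and 375 per arm comes out just under 80%, not above it.

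The opt-out sentence then looks empty. Its word 'also' suggests patients added beyond the power calculation, yet that calculation already uses all 750. Two thirds of patients enter through the route where opt-out is possible, and opt-outs stay in arm 2, so the primary comparison will carry some dilution. At stake is how a null result is read: as coming from a trial with more than 80% power and an opt-out margin, when it might have neither.

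**Working it through.** **Inputs from the documents.** n = 375 per arm; two-sided alpha 0.05 (z = 1.960); difference d = 0.10, read as absolute; late phase 500/750 = 2/3 of patients. The calculation takes all randomised patients as the denominator.

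**Inputs not in the documents.** Control composite rate p and late-phase opt-out proportion q. Both are varied below.

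**Step 1: the plan's own figure.** With p₂ = p + d and p̄ = (p + p₂)/2,

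power = Φ{ [d − 1.960·√(2p̄(1−p̄)/n)] / √([p(1−p) + p₂(1−p₂)]/n) }.

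- Control 40%: (0.10 − 0.0712)/0.0361 = 0.796, so power is 78.7%.
- Control 30%: (0.10 − 0.0683)/0.0346 = 0.916, so power is 82.0%.

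| Control rate | Share of attenders good/excellent, at 50% show | Power, formula | Power, exact chi-squared | Total N for 80% |
|---|---|---|---|---|
| 25% | 50% | 85.0% | 85.1% | 658 |
| 30% | 60% | 82.0% | 82.2% | 712 |
| 35% | 70% | 79.9% | 79.7% | 752 |
| 40% | 80% | 78.7% | 79.2% | 776 |
| 45% | 90% | 78.3% | 79.0% | 784 |
| 50% | 100% | 78.7% | 79.2% | 776 |

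Power crosses 80% at control rates of 34.8% and 55.2%. The upper crossing is out of reach if only about half of patients attend. The largest shortfall is 80 − 78.3 = 1.7 points by formula and 80 − 79.0 = 1.0 point by exact calculation. At 80% power the detectable difference for control rates of 35% to 50% is 10.0 to 10.2 points. A continuity correction, which the plan does not specify, would lower the formula figures there to 76.1–77.8%.

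**Step 2: absolute or relative.** A relative 10% difference at control rates of 35% to 50% would have only 17% to 28% power. The absolute reading is the one that fits the plan's figure.

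**Step 3: opt-outs, if the 10 points are undiluted.** Assume opt-outs gain nothing. The effect becomes 10 × (1 − 2q/3) points.

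- q = 10%: 10 × (1 − 0.0667) = 9.33 points; power 72.5% to 74.4% at control rates of 35% to 50%.
- q = 20%: 8.67 points; power 66.1% to 68.1%.
- At a control rate of 30%, 80% power survives up to about 4% late-phase opt-out; at 25%, up to about 10%.

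**Step 4: opt-outs, if the 10 points are already diluted.** The Initial Statistical Analysis Plan worked with a 15% difference and a target of 400. The Summary of Protocol Changes logs the new sample size and the early/late split in one modification (4/4/2019), and the final plan then has a 10% difference and 750 patients. Take 15 points as the undiluted effect:

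- q = 10%: 15 × (1 − 0.0667) = 14 points; power about 97% at control rates of 35% to 50%.
- The effect falls to 10 points only when 15 × (1 − 2q/3) = 10, that is, q = 50%.

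On this reading the allowance exists and is generous.

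**The case for a change.** The strongest case for acting rests on the opt-out sentence. The text assigns 10 points to 750 patients and only afterwards says that opt-outs would shrink the effect. In that order, the 10 points look undiluted. At control rates of 35% to 50%, 752 to 784 patients are needed before any opt-out, so 750 holds no reserve; at 30% the reserve is 750 − 712 = 38 patients. A reader cannot check either claim from what is written, and a correction would cost only wording.

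Part of this stands. The control rate, the opt-out rate, and whether the 10% is absolute and before or after dilution are all missing. If the control rate is 35% to 50% and the 10 points are undiluted, there is no margin.

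It does not stand as an error. It needs a control rate the documents do not give, a reading of the opt-out sentence they do not settle, and opt-out rates of 10% or 20% with no benefit in opt-outs, which are illustrations only. The plan says the calculation drew on pilot data, and those inputs are not shown, so the stated power cannot be shown to be wrong. Nor will readers be left guessing afterwards: the late-phase opt-out proportion is a listed secondary outcome, and the control rate will be visible in the results.

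**Conclusion.** The concern does not call for a change. The arithmetic behind it is right, but it does not contradict the plan. For an absolute 10-point difference with 375 per arm, power exceeds 80% when the control composite is below about 34.8%. Between there and 50% it is 78.3% to 79.9% (79.0% to 79.7% by exact calculation at 35% to 50%). A gap of at most 1.7 points against a rounded target would not alter how a null result is read.

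Whether the size includes an opt-out allowance depends on an ambiguity. There is little or none if the 10 points are undiluted and the control rate is about 30% or more, and ample room if 10 points is a reduced version of the initial 15.

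This rests on the pooled two-proportion calculation without continuity correction, all randomised patients in the denominator, and a show rate of about 50% in usual care. The unstated assumptions are a reporting gap. Filling it would leave the 750 patients, the chi-squared test and the intention-to-treat handling of opt-outs as they are.

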#### **Secondary outcome variable(s)**

Secondary outcomes of the study will include colonoscopy show rate, bowel preparation quality (rescue, poor, fair, adequate, good, excellent; we will also collect Boston Bowel Prep Score if available [scale 0-9]), colonoscopy cancellation rate, timing of advance cancellation notification (days), colonoscopy reschedule rate, and colonoscopy appointment no-show rate. A colonoscopy "show" will be defined as a patient who attends their originally scheduled colonoscopy appointment. A "cancellation" will be defined as an appointment that is canceled at least one day prior to the originally scheduled colonoscopy appointment date. A "reschedule" will be defined as an appointment that is canceled and rescheduled (for a future date) on the same day, at least one day prior to the originally scheduled colonoscopy appointment date. Finally, as an additional secondary outcome, we will also collect the proportion of patients who opt out of the texting program in the late phase of enrollment (described below).

Formatted: Font color: Black

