**Deleted:** Patients who have a physician order for a colonoscopy will call the PPMC call center in order to schedule their procedure. At this time, the call center staff will screen the patient for eligibility (age criteria and text messaging ability) and will explain the details of the study following a pre-determined script. Patients who agree to participate in the study will have their cell phone number recorded. A list of these patients will be forwarded to the clinical research coordinator on a weekly regular basis, who will confirm patient eligibility and then manually enter patients into the WTH platform for randomization. Alternatively,

**Deleted:** for

Randomization - Phase 2: In the early phase, using a random number generator in the WTH platform, patients will be 1:1 randomized to arm 1 or arm 2. Beginning in the late phase of enrollment, patients will be randomized to arm 1 or arm 2 in a 1:1 ratio in variable blocks of 8 and 4 using the WTH platform, until the target sample size of 375 patients per arm is reached.

**Deleted:** between 500 and

**Deleted:** 6

**Deleted:** 40

**Deleted:** , until the target

**Deleted:** sample size of 200 patients per arm is reached. Randomization will be performed and recorded in WTH.

Chart review - Phase 3: after randomization and in tandem with phase 4 (below), the research coordinator will perform a chart review to obtain patient demographic and comorbidity data (hypertension, hyperlipidemia, diabetes, inflammatory bowel disease, obesity, active opiate prescription). We will also collect data on the number of patients opting out in the late phase of enrollment, as well as data on nursing phone calls which are performed as a component of usual care (not called, called but could not reach patient, called and spoke with patient). All data will be inputted into and stored in a secured RedCap database. Only key study staff will have access to the RedCap database, which is stored on a secure firewall-protected server.

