#### **Analysis Plan**

Descriptive analysis will include comparison of baseline demographics and major medical comorbidities between study arms. Continuous and categorical data will be compared using the Wilcoxon Rank-sum and Chi-squared tests, respectively. An alpha threshold of 0.05 will be used for statistical significance, with two-tailed testing performed in all instances. For the primary analysis, we will perform a Chi-squared test of independence to compare the proportion of colonoscopies with good/excellent bowel preparation between groups. In the secondary analysis, Chi-squared tests of independence will be performed to compare colonoscopy status (show, no-show, reschedule, cancellation) as well as bowel preparation quality (excellent, good, adequate, fair, poor) between groups. Among canceled colonoscopies, median lead time of cancellation will be compared between groups using the Wilcoxon Rank-sum test. Finally, for both primary and secondary analyses, we will consider multivariable regression modeling to adjust for imbalances in possible confounders, if present despite randomization.

**Deleted:** Finally, a

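### Show rate is a listed secondary outcome, but the SAP specifies no comparison or estimate for it, only a test of a four-level status variable; preparation grade is tested without using its order

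*Combined protocol and SAP*

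**What the plan says.** The Final Protocol, under Secondary outcome variable(s), opens its list with "Secondary outcomes of the study will include colonoscopy show rate, bowel preparation quality" and goes on to name cancellation, reschedule and no-show rates as further separate items. It defines a show, a cancellation and a reschedule.

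The Analysis Plan of the Final Protocol gives this analysis: "Chi-squared tests of independence will be performed to compare colonoscopy status (show, no-show, reschedule, cancellation". The Final Statistical Analysis Plan repeats it and adds preparation grade in the same sentence: "compare colonoscopy status (show, no-show, reschedule, cancellation) as well as bowel preparation quality (excellent, good, adequate, fair, poor) between groups".

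The significance rule is general: "An alpha threshold of 0.05 will be used for statistical significance, with two-tailed testing performed in all instances". No multiplicity rule is given for secondary outcomes. Regression is only to be considered if confounders are imbalanced, and no model is named. A rank-sum test is planned for cancellation lead time but not for preparation grade.

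**The concern.** The outcome list and the analysis do not match. Four rates are listed, but the stated analysis is of one status variable with four levels. As naturally read this is a 2×4 table with 3 degrees of freedom. Such a test asks whether the two arms differ anywhere in the distribution of status. It does not say which rate moved or in which direction, and it gives no effect size.

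This matters most for show rate, which is in the trial's title and in its second aim. A significant status test could come entirely from patients moving between kinds of non-attendance, with attendance unchanged. That is plausible for a reminder programme that also gives a phone number. If the choice between one test and four is left open, it can be made after the data are seen.

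Preparation grade is an ordered outcome, but a chi-squared test of independence treats its levels as unordered names. If texting shifts grades consistently upward, that test uses the data less efficiently than one that respects the order.

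**Working it through.** **Inputs from the documents**
- Arms: "375 in arm 1 (usual care) and 375 in arm 2 (usual care plus texting intervention".
- Alpha 0.05, two-sided (Final Statistical Analysis Plan).
- Only baseline rate given (Background): "colonoscopy show rates as compared to baseline values at PPMC (90% versus ~50" per cent. So about 50% is the documented baseline show rate.

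**Assumptions, because the documents give no figures**
- Control split of status: show 50%, no-show 20%, reschedule 15%, cancel 15%.
- Preparation grades and numbers attending, as stated in step 4.

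**Step 1. The plan's own figure.** The plan states that "a total sample size of 750 patients will have greater than 80% power to detect a 10% difference in the primary outcome". It gives no control rate. With 375 per arm and a 10-point gain, the two-proportion formula gives 88.7% at a control rate of 20%, 82.0% at 30%, 78.3% at 45% (the minimum), 78.7% at 50%, 82.0% at 60% and 88.7% at 70%. The claim is reproduced to within 2 points throughout. It concerns the primary outcome only, and nothing below changes it.

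**Step 2. What a significant status test means.** For n per arm, the non-centrality is λ = n × Σ (p₁ − p₂)² / (p₁ + p₂), summed over categories. The 5% critical values are 7.815 (3 df) and 3.841 (1 df).

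Suppose no-shows fall from 20% to 10%, and reschedules and cancellations each rise from 15% to 20%. Show rate stays at 50%.

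λ = 375 × (0 + 0.01/0.30 + 0.0025/0.35 + 0.0025/0.35) = 17.86. Power at 3 df is about 96%.

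The test is nearly always significant although attendance has not changed.

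**Step 3. Power for a 10-point gain in show rate (50% vs 60%).** The 1-df test of show against not-show has λ = 375 × (0.01/1.10 + 0.01/0.90) = 7.58, so power is 79%. The 3-df test depends on where the gain comes from:

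| Source of the 10 points | λ | Power, 3 df |
|---|---|---|
| All three categories in proportion (16/12/12%) | 7.58 | 63% |
| 7 points from the 20% category, 1.5 from each other | 9.57 | 74% |
| 5 points from the 20% category, 5 from one 15% category | 9.84 | 75% |
| All from the 20% category | 15.91 | 93% |
| All from one 15% category | 22.16 | 99% |

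The proportional case is the floor: there λ equals that of the 1-df test, and any other split raises it. In that case, at baselines of 60% and 70%, power is 66.9% vs 82.0% and 76.1% vs 88.7%.

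**Step 4. Preparation grade.** Attenders: 375 × 0.50 ≈ 188 and 375 × 0.60 = 225. Assumed control grades, excellent to poor: 20/45/15/12/8%. With a common odds ratio of 1.5, simulation gives about 39% to 40% for the five-category chi-squared test and 60% to 61% for rank-sum. Across three other assumed distributions, with 188 to 300 graded per arm, the ranges are 35% to 60% and 57% to 80%.

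A non-monotone change reverses this. For 5/10/15/45/25% (poor to excellent) against 2/8/25/45/20%, with 225 per arm, the nominal test has about 73% and rank-sum about 15%.

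**Step 5. Multiplicity if all four rates were tested.** Four independent tests at 0.05 would give 1 − 0.95⁴ = 18.5% familywise error. The four rates are not independent, so this is only a guide. Bonferroni at 0.05/4 = 0.0125 would cut show-rate power at 50% vs 60% to about 60%, below the 63% floor in step 3.

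**The case against.** **The text does not say there is one test.** It uses the plural, never mentions one table or 3 df, and does not exclude a test for each rate. This stands. The plural is equally satisfied by one test for status and one for grade, so what can be said is that no show-rate comparison is specified. A reader might infer that the plan rules one out; the wording does not support that.

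**Loss of power is not general.** A reader might infer that the 3-df test is always weaker. Step 3 shows it is stronger when one category supplies the whole gain. For grade, the advantage of an ordered test rests on a consistent shift. Both objections stand, so the main argument is interpretation, with power secondary.

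**Four separate tests bring their own problem.** Without a multiplicity rule they inflate error, and with Bonferroni the power advantage disappears. This stands and shapes the fix.

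**An ordered test needs an agreed order.** The Final Protocol's outcome list includes *rescue*, which the SAP's list omits, and *adequate* is not placed relative to *fair* and *good* by any definition. Grades exist only for patients who attend, and the plan does not say how non-attenders enter this comparison. These gaps must be closed first.

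**The planned tests are valid, and rates can be read from the counts.** True, but which comparison carries the show-rate conclusion should be fixed in advance.

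**Conclusion.** The point holds as a mismatch between listed outcomes and specified analyses. Show rate, part of the title and second aim, has no comparison, estimate or confidence interval written for it, and the status test as naturally read cannot supply one. In the worked example that test is significant about 96% of the time with show rate unchanged. That figure rests on an assumed 50/20/15/15% split and a halving of no-shows; only the 50% is anchored in the documents.

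Power runs from 63% to 99% for the status test against 79% for a direct show-rate test, depending on the source of the gain. For grade, an ordered test gains about 20 points under the assumed consistent shift and loses under a non-monotone one.

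Two further readings are not supported. A reader might infer that separate tests were dropped on amendment; the Initial Statistical Analysis Plan has the same form, with three status levels. A reader might also infer damage to the primary result; the binary primary outcome, its 1-df test and the sample size are unaffected. This is a worthwhile improvement to secondary analyses.

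**What to change.** In the Final Protocol's Analysis Plan and the Final Statistical Analysis Plan:

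1. Name show rate as the key secondary outcome. Compare it over all randomised patients with a 1-df chi-squared test, and report the risk difference with a 95% CI. At 50% vs 60% the half-width would be about 1.96 × √((0.25 + 0.24)/375) = 7.1 points.
2. Report no-show, reschedule and cancellation rates over all randomised patients as risk differences with 95% CIs, without confirmatory claims. This avoids a four-way correction.
3. Keep the four-category status table as descriptive.
4. Compare preparation grade with a rank-sum or linear-trend test. First state the category order and reconcile the two lists, including *rescue* and *adequate*. State also that the comparison covers attenders only and is therefore not protected by randomisation.

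The cost is wording and somewhat more reporting; no new data are needed. The price is less sensitivity to non-monotone changes in grade, which the full table of grades by arm would still show.
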